3.4.2 Study Design

This will be a retrospective database study using IMS Brogan's LRx dataset, in which de-identified patient level prescription information will be used to evaluate adherence to the labeling recommendations for exenatide use in Canada. The study will be based on a 'Look-Back,' 'Analysis' and 'Follow-Up' period as shown in figure 1. Patients will be selected for the study if they are receiving a Byetta prescription in the 12 month analysis period.

[figure not shown]
The 'Look-back' period is used to ensure that each patient within the analysis period has at least 6 months of data prior to first Byetta script. This eligibility period ensures that a patient whose first Byetta script occurs at the start of the analysis period can be classified appropriately and that they are present in the database prior to the first script. Similarly, the 'Follow-up' period is used to ensure that each patient has at least 3 months of data following the last script within the analysis period. This ensures that the duration of therapy for a patient who receives their last script at the end of the analysis period is accounted for and can have their therapy appropriately classified, specifically around the concomitant use of Byetta with insulin or TZDs.

Figure 1: Study periods proposed for analysis of Byetta use in the 1st year post launch

In addition to the study period proposed in figure 1, the analysis will be conducted for Year 1, 2 and 3 post Byetta launch allowing for an analysis of trends in Byetta use over time, as shown in figure 2. Study 1* will provide results on Year 1 and 2 and would commence at the availability of Aug 2013 data. Study 2** will provide Year 3 results and would commence at the availability of Aug 2014 data.

Figure 2: Three proposed analysis periods for study post Byetta Launch

Note: Implies that the look-back period and the follow-up period are at least 6 months and 3 months for each patient, respectively.

Note: Month 1 = Date of First Byetta Sale = June 2011

*Study 1: All Byetta prescriptions in the database in months 0-24, post launch

** Study 2: All Byetta prescriptions in the database in months 25-36, post launch

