3.4.3 Study Population

Inclusion/Exclusion Criteria:

All patients in the LRx database who have been prescribed Byetta in Canada during the analysis period will be included in the study. Patients with inconsistent records and/or insufficient data, as shown in table 3, will be omitted to restrict the analysis to a consistent and robust patient sample.

Exclusion criteria are required since the pharmacy data (LRx) is driven through data entry at the individual stores. The criteria are used to filter out transactions that either have entry mistakes or have place-holder information that is not accurate. The exclusion criteria are established to ensure a consistent record for patients in the study sample. Inclusion and exclusion criteria may be modified during the initial stages of the project.

Table 3: Exclusion criteria applied to remove patients with inconsistent Rx history

Criteria	Conditions for Exclusion	Rationale
Demographic Criteria	Patients without a consistent year of birth, province, or gender	Patients without a consistent demographic record of gender, year of birth and province are not reliable due to inconsistencies
Constant Store Criteria	Patients at stores with inconsistent reporting after May 2011	Stores with inconsistent recorded information will not have accurate information on what prescriptions a patient received
Max Rx Criteria	Patients with more than 208 Rx/year	This is to eliminate pharmacist error
Min Rx Criteria	Patients with fewer than 6 Rx	Patient with less than 6 prescriptions are excluded because there is the potential for including the same patient multiple times as occasionally patients fill prescriptions at different pharmacies when traveling or for convenience
Consistent Patients	Remove patients without any prior Rx at a store	Removing patients without any other prior prescriptions at a store also eliminates patients who have changed pharmacies and may be included multiple times in the data
Analysis Period	Remove patients without any	Patients who do not have a prescription

	Rx in the Analysis Period	in the analysis period cannot be included as they do not have any prescriptions to analyze
12 Month Gap	Remove patients with a year gap between Diabetes Rx	Patients with a year gap between diabetes prescriptions are likely to have filled prescriptions at an alternative pharmacy and could be counted multiple times in the data set

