3.4.4 Study Outcomes and Definitions

[figure not shown]
The primary outcome of interest is the off label use of Byetta in Canada.

A patient's therapy type will be inferred by identifying if a patient switches between, or adds on to therapies, as shown in figure 3.

Mono Therapy is defined as a patient receiving a specific therapy (Therapy 1) prior to a different therapy (Therapy 2) where Therapy 1 is not detected after Therapy 2 initiation. Mono therapy for this study, refers to a patient received a prescription for only one product at a given time.

Concomitant Therapy is defined as a patient receiving a specific therapy (Therapy 1) prior to a different therapy (Therapy 2) where Therapy 1 is detected after Therapy 2 initiation.

Figure 3: Distinguishing between add-on and switch therapies

Patients will be selected for the study if they receive a Byetta script anytime during the analysis period and if they met the inclusion criteria. To identify on-label vs. off-label use, patient history will then be used to classify patients as "inferred on-label" if they also received Metformin and/or SU or Lantus during the study (Business rules 1 and 2 in Table 5).

All other patients that do not meet the criteria for use of Byetta with metformin and/or SU or Lantus will be classified as “inferred off-label”. The group of patients classified as “inferred off-label” will then be further classified to gain a better understanding of the trends in “inferred off-label” use of Byetta (Business rules 3-10 in Table 5).

The Business rules described in Table 5 are prioritized to ensure the appropriate classification of each patient. Therefore patients will be classified based on the highest rank business rule. For example, if a patient receives scripts for both Metformin and other insulin during the analysis period, they will be classified as “inferred on-label” as they have a script for metformin and therefore are classified by business rules 1 and 2

Note: The patient classification categories (‘Inferred Adherence Label’) can be modified in the initial phase of the project.

Table 5: Business rules applied to classify patients as “on-label” vs. “off-label”

(The business rules have been structured to align with the Canada monograph for Byetta indication and clinical use (see Table 1) and will be finalized upon study initiation).

Rank	Business Rules	Cohort Description	Inferred Adherence Label

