3.4.5 Sample Size

All patients in the LRx database who have been prescribed Byetta in Canada during an analysis period and met the inclusion criteria will be included in the study. In similar studies in this market ~500,000 patient records have passed selection criteria for inclusion to a study sample. However the anticipated use of Byetta amongst this patient population in the first year of marketing in Canada is unknown at the present time and is projected to be modest. Upon initiation of the study, IMS Brogan will analyze the dataset to identify the number of patients available for study (the number of patients on Byetta in the analysis period). The number of Byetta patients is expected to rise in each year analyzed.

To allow for sufficient patients for a robust analysis, we will perform the first study 2 years after Byetta's launch in Canada, analyzing the two years separately (see figure 2). The analysis will be repeated in the subsequent year, to capture additional Byetta patients and identify shifts in Byetta usage.

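### Years 1-2 and Year 3 come from different data cuts, with no re-run and no stated lock on the rules, so a shift between them could partly reflect method

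*Protocol*

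**What the plan says.** Comparison across years is a stated purpose. Section 3.4.2 (Study Design) plans separate analyses for Years 1, 2 and 3, "allowing for an analysis of trends in Byetta use over time". Section 3.4.5 (Sample Size) adds: "The analysis will be repeated in the subsequent year, to capture additional Byetta patients and identify shifts in Byetta usage".

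The data cuts differ. In 3.4.2, "Study 1* will provide results on Year 1 and 2 and would commence at the availability of Aug 2013 data", and "Study 2 will provide Year 3 results and would commence at the availability of Aug 2014 data". The note to Figure 2 confines Study 2 to months 25-36, so it contains no second computation of Years 1 and 2.

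The Constant Store row of Table 3 (3.4.3 Study Population) removes "Patients at stores with inconsistent reporting after May 2011". It gives a starting point and no end date.

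Two clauses leave definitions open. In 3.4.3, "Inclusion and exclusion criteria may be modified during the initial stages of the project". In 3.4.4 (Study Outcomes and Definitions), the classification categories "can be modified in the initial phase of the project". The lead-in to Table 5 says that the business rules become final when the study is initiated. Section 3.4.5 places a count of available Byetta patients at initiation too. The protocol does not say which comes first, and it does not say whether the version used in Study 1 also governs Study 2.

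**The concern.** A trend statement needs every year measured on the same basis. Here Years 1 and 2 share one extract, and Year 3 stands alone on another taken a year later. Two things can differ between them besides prescribing:

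- **The store panel.** A consistency test with a fixed start and an open end becomes harder to pass as the extract lengthens.
- **The rules.** The on/off-label categories define the primary outcome. Nothing in the text fixes one dated version for both studies.

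The study answers a Health Canada request about use outside the label. If the off-label percentage moves in Year 3, the sponsor should be able to say whether prescribing changed. As written, the protocol gives no way to separate that from a change of panel or rules.

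**Working it through.** **Step 1: reproduce the stated data cuts.** Inputs from 3.4.2: Month 1 is June 2011, each analysis period is 12 months, and follow-up is at least 3 months.

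| Year | Months | Calendar | Plus 3 months |
|---|---|---|---|
| 1 | 1-12 | Jun 2011 - May 2012 | Aug 2012 |
| 2 | 13-24 | Jun 2012 - May 2013 | Aug 2013 |
| 3 | 25-36 | Jun 2013 - May 2014 | Aug 2014 |

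Both stated cuts, August 2013 and August 2014, are reproduced.

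**Step 2: length of the store test.** Assume that the test runs from June 2011 to the data cut of each study. The protocol does not state this; it follows from a fixed start with no end.

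- Study 1: June 2011 to August 2013 = 24 + 3 = 27 months.
- Study 2: June 2011 to August 2014 = 36 + 3 = 39 months.

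The difference is 12 months. A store that first lapses between September 2013 and August 2014 passes in Study 1 and fails in Study 2. Its patients count in Years 1-2 but not in Year 3.

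**Step 3: size of the store effect.** The protocol gives no lapse rate and no off-label rate by store, so these are assumed ranges. Let h be the share of stores becoming inconsistent per month.

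- Share passing: (1 - h)^27 in Study 1 and (1 - h)^39 in Study 2.
- Share of Study 1 stores lost by Study 2: l = 1 - (1 - h)^12.
- Let off-label use be constant over time, at p_K in kept stores and p_L in lost stores, with equal Byetta patients per store. Years 1-2 then show (1 - l)p_K + l p_L, and Year 3 shows p_K. The artificial shift has size l x |p_L - p_K|.

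| h per month | Pass, Study 1 | Pass, Study 2 | l | Shift if stores differ by 5 / 10 / 20 points |
|---|---|---|---|---|
| 0.2% | 94.7% | 92.5% | 2.4% | 0.12 / 0.24 / 0.47 |
| 0.5% | 87.3% | 82.2% | 5.8% | 0.29 / 0.58 / 1.17 |
| 1% | 76.2% | 67.6% | 11.4% | 0.57 / 1.14 / 2.27 |

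The range is about 0.1 to 2.3 percentage points. It is zero if lost and kept stores have the same off-label share.

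**Step 4: size of a rule effect.** If a rule change relabels x% of patients in one direction, the off-label percentage moves by x points. For example, relabelling Rank 2 of Table 5 would move exactly the Rank 2 share: patients with evidence of metformin, a sulfonylurea or Lantus but no concomitant use. The protocol gives no estimate of that share, and nothing in it suggests this change is planned. The example shows only that a rule change could outweigh the store effect.

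**The case against.** The strongest reply has four parts.

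1. **The modification clauses speak of one project.** A reader might infer that the rules can be reopened at the start of each study. The text does not say so. Both clauses refer to a single project, the analysis is described as a repeat, and Table 5 has a stated point at which its rules become final. This stands. What remains is a gap: the protocol neither carries the Study 1 version into Study 2 nor rules out a new one.

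2. **Nothing says that rules change after results are seen.** A reader might infer that definitions may be adjusted once the data are open, and so that a favourable off-label figure could not be defended to the regulator. The documents do not support this. Finalization and the patient count both fall at initiation, with no order given, and the count's stated purpose is only to establish how many Byetta patients are available. What stands is that the order should be written down.

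3. **The extra store lapses fall in Year 3's own window.** September 2013 to August 2014 lies inside Year 3 plus its follow-up (June 2013 to August 2014). A test defined per year would also exclude those stores from Year 3, for the reason Table 3 itself gives. This stands. The panel difference arises only because the same stores remain in Years 1-2, where their data were sound. It is a matter of comparability and does not make Year 3 wrong.

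4. **The trend is descriptive, and a statistical analysis plan may settle the details.** The analysis section plans tables for each year, with no test or contrast between years. A plan that is not shown could fix the store window and the rule version. Even so, the two-cut design and the permission to modify are set in the protocol itself, alongside the aim to "identify shifts in Byetta usage".

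**Conclusion.** The point holds as a comparability weakness in the year-to-year reading. The protocol states a trend aim, computes Years 1-2 and Year 3 on different cuts without a re-run, leaves the store test open-ended, and does not state that one version of the criteria and categories is locked before classification and used in both studies. A Year 1-2 versus Year 3 shift could therefore partly reflect panel or rule differences.

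The store effect alone is probably small: about 0.1 to 2.3 points. That rests on three assumptions: a test running to each cut, 0.2% to 1% of stores lapsing per month, and a 5 to 20 point off-label difference between lost and kept stores. A rule change cannot be sized from the document, but it is limited to the share of patients relabelled. It would be wrong to call it unbounded.

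The split cut does not affect the percentages within any one year, and Years 1 and 2 already share an extract.

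**What to change.** 1. Finalize and date Tables 3 and 5 before any Byetta patient is classified. Limit the feasibility step to the total Byetta count. State that the same version applies in Study 2.
2. In Study 2, re-run Years 1 and 2 on the August 2014 extract with the same store panel and rule version as Year 3, and base trend statements on that run. Keep each year's own look-back, 12-month analysis and follow-up windows. Otherwise the data available after the end of each year would be unequal: 39 - 12 = 27 months for Year 1, 39 - 24 = 15 for Year 2 and 39 - 36 = 3 for Year 3. The Table 5 footnote counts evidence from the look-forward period, so this would introduce a new imbalance.
3. If a rule has to change after the lock, report all years under both the locked and the changed version.

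The cost is a few sentences in the protocol and a re-run of existing code on two earlier years. The downside is that the Year 1-2 figures in the second report may differ slightly from those in the first and will need a sentence of explanation.

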3.4.3 Study Population

Inclusion/Exclusion Criteria:

All patients in the LRx database who have been prescribed Byetta in Canada during the analysis period will be included in the study. Patients with inconsistent records and/or insufficient data, as shown in table 3, will be omitted to restrict the analysis to a consistent and robust patient sample.

Exclusion criteria are required since the pharmacy data (LRx) is driven through data entry at the individual stores. The criteria are used to filter out transactions that either have entry mistakes or have place-holder information that is not accurate. The exclusion criteria are established to ensure a consistent record for patients in the study sample. Inclusion and exclusion criteria may be modified during the initial stages of the project.

Table 3: Exclusion criteria applied to remove patients with inconsistent Rx history

Criteria	Conditions for Exclusion	Rationale
Demographic Criteria	Patients without a consistent year of birth, province, or gender	Patients without a consistent demographic record of gender, year of birth and province are not reliable due to inconsistencies
Constant Store Criteria	Patients at stores with inconsistent reporting after May 2011	Stores with inconsistent recorded information will not have accurate information on what prescriptions a patient received
Max Rx Criteria	Patients with more than 208 Rx/year	This is to eliminate pharmacist error
Min Rx Criteria	Patients with fewer than 6 Rx	Patient with less than 6 prescriptions are excluded because there is the potential for including the same patient multiple times as occasionally patients fill prescriptions at different pharmacies when traveling or for convenience
Consistent Patients	Remove patients without any prior Rx at a store	Removing patients without any other prior prescriptions at a store also eliminates patients who have changed pharmacies and may be included multiple times in the data
Analysis Period	Remove patients without any	Patients who do not have a prescription

	Rx in the Analysis Period	in the analysis period cannot be included as they do not have any prescriptions to analyze
12 Month Gap	Remove patients with a year gap between Diabetes Rx	Patients with a year gap between diabetes prescriptions are likely to have filled prescriptions at an alternative pharmacy and could be counted multiple times in the data set
6-month look back data	Remove patients without 6 months of data prior to first Byetta script	Ensures all patients are present in the dataset and have a consistent record for analysis
3-month Follow-up data	Remove all patients without 3 month follow-up data	Ensures patients therapy can be appropriately classified as add-on or switch

To identify other diabetes therapies for the selected patients, prescriptions for product groups in table 2 will also be tracked for selected patients

Table 4: Diabetes therapies tracked for Byetta patients

Category	Product Group	Product
Insulin	Premix Human	Lilly Human Premix, NNCI Human Premix
	Premix Analog	Humalog Mix, NovoMix
	Basal Human	Novolin NPH, Humulin N
	Basal Analog	Lantus, Levemir
	Rapid Human	Humulin R, Novolin Toronto
	Rapid Analog	Apidra, Humalog, NovoRapid
OAD	Metformin	Metformin
	Sulfonylurea (SU)	Diamicon / Diamicon MR, Gliclazide, Glimepiride/ Amaryl, Glyburide
	Thiazolidinedione (TZD)	Avandamet, Avandaryl, Actos, Avandia, Generic Pioglitazone
	PPG Regulators	GlucNorm, Starliz, Generic Repaglinide
	DPP4	Januvia, Onglyza, Janumet, Trajenta

	Prandase	Prandase
GLP1	GLP1	Victoza, Byetta

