1	Concomitant use of* Byetta with metformin (met) and/or sulfonylurea (SU), OR Concomitant use of Byetta with Lantus	Met and/or SU or Lantus is prescribed with Byetta	Inferred On-label
2	Evidence of** Byetta and metformin and/or sulfonylurea OR Evidence of Byetta and Lantus	Met and/or SU or Lantus is not prescribed with Byetta, but both appear in the analysis period	Inferred On-label
3	Evidence of Byetta and Levemir	Levemir is prescribed in the analysis period	Off-Label Insulin Use
4	Evidence of Byetta and Human Basal Insulin	Human basal insulin is prescribed in the analysis period	
5	Evidence of Byetta and thiazolidinedione (TZD)	TZD is prescribed in the analysis period	Off-Label OAD Use

6	Byetta Alone	No other products prescribed in the analysis period	Inferred Off-label
7	Evidence of Byetta and all other insulin	Other insulin is prescribed in the analysis period	
8	Evidence of Byetta and all other OADs	Other OADs are prescribed in the analysis period	
9	Pediatric Patients	Patient is under the age of 18 (<18)	
10	All other combinations	All other combinations	

Note: Evidence of Diabetic ketoacidosis, diabetic coma/precoma and end stage renal disease cannot be inferred from the dataset; therefore we will not be able to identify these patients as a separate group

* "Concomitant use of..." refers to continued use of Byetta and other product

** "Evidence of..." refers to anytime within the study period including look-back or look forward periods

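### Table 4 gives each combination tablet a single drug group, so patients whose only metformin or sulfonylurea comes in such a tablet are counted as off-label

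*Protocol*

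**What the plan says.** Protocol section 3.4.3 lists the tracked diabetes therapies in Table 4, with one group per product. The sentence that introduces the table says that "prescriptions for product groups in table 2 will also be tracked for selected patients". The table number there looks like a slip, because Table 2 is the regional coverage table and the product groups are in Table 4.

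- TZD group: "Avandamet, Avandaryl, Actos, Avandia, Generic Pioglitazone".
- DPP4 group: "Januvia, Onglyza, Janumet, Trajenta".
- SU group: "Diamicon / Diamicon MR, Gliclazide, Glimepiride/ Amaryl, Glyburide".
- Metformin group: one entry, metformin itself.

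Avandamet, Avandaryl and Janumet each appear once and in no other group.

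Section 3.4.4 then classifies patients by the ranked rules of Table 5. The rank 1 cohort is described as "Met and/or SU or Lantus is prescribed with Byetta". Rank 2 accepts the same drugs without continued joint use. Both are on-label. Rank 3 takes Levemir and rank 5 takes TZDs. Rank 8 is "Evidence of Byetta and all other OADs". The highest rank that applies decides, and anyone who does not meet the metformin, SU or Lantus criteria is off-label by default. A footnote to Table 5 lets evidence of a drug come from any point in the study period, look-back and follow-up included. The rules are said to follow the monograph indication in Table 1 and are to be finalised when the study starts.

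**The concern.** Table 1 expresses the indication in terms of drugs: metformin and/or an SU, or insulin glargine. Table 4 sorts products. A product with two ingredients but one group loses one ingredient before the rules are applied. Two patients exposed to the same drugs can then get opposite labels because one was dispensed two tablets and the other a combined one.

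The proportion off-label is the primary outcome and answers a regulator's request. Under group matching the error runs one way, towards more off-label use. It also bears on the trend across Years 1 to 3: a change in the use of combination tablets would look like a change in adherence to the label.

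**Working it through.** **Inputs.** The groups come from Table 4, and the rules, their order and the default from Table 5 and section 3.4.4. One input is assumed because the protocol does not state it: Avandamet contains metformin and a TZD, Avandaryl an SU and a TZD, and Janumet metformin and a DPP4 agent. The protocol gives no figure to reproduce.

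**Step 1: paired regimens.** Each regimen is Byetta plus the products shown and nothing else in the study period. It is classified first by the Table 4 group, then by ingredient.

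| Byetta plus | By product group | By ingredient |
|---|---|---|
| Janumet | rank 8, off-label | rank 1/2, on-label |
| Januvia + metformin | rank 1/2, on-label | rank 1/2, on-label |
| Avandamet | rank 5, off-label OAD | rank 1/2, on-label |
| Avandia + metformin | rank 1/2, on-label | rank 1/2, on-label |
| Avandaryl | rank 5, off-label OAD | rank 1/2, on-label |
| Avandia + glimepiride | rank 1/2, on-label | rank 1/2, on-label |
| Levemir + Janumet | rank 3, off-label insulin | rank 1/2, on-label |
| Levemir + Januvia + metformin | rank 1/2, on-label | rank 1/2, on-label |
| Avandamet + metformin | rank 1/2, on-label | rank 1/2, on-label |
| Janumet + gliclazide | rank 1/2, on-label | rank 1/2, on-label |
| Janumet + Lantus | rank 1/2, on-label | rank 1/2, on-label |

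The first eight rows form four pairs, and each pair disagrees under group matching and agrees under ingredient matching. The Levemir pair shows that the insulin category is touched too. The last three rows mark the limit: one separate metformin, SU or Lantus script anywhere in the window gives the on-label result either way.

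**Step 2: effect on the primary outcome.** Let T be the off-label proportion under ingredient matching. Let F be the share of Byetta patients who have a combination tablet containing metformin or an SU and no separate metformin, SU or Lantus script from look-back to follow-up. Then

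reported off-label = T + F.

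The protocol gives neither T nor F. With assumed values, for illustration only:

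| T | F = 1% | F = 5% | F = 10% |
|---|---|---|---|
| 10% | 11% | 15% | 20% |
| 20% | 21% | 25% | 30% |

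For the trend, if T stayed at 20% while F rose from 1% to 5%, the reported figure would go from 21% to 25% with no change in the drugs taken with Byetta.

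**Step 3: effect on Table 7.** The Metformin row misses every patient whose only metformin is in Janumet or Avandamet. The SU row misses every patient whose only SU is in Avandaryl. Neither condition excludes patients who are on-label through another drug. Janumet + Lantus and Janumet + gliclazide are classified correctly in Table 6 but drop out of the Metformin row. Avandaryl + metformin drops out of the SU row. The Table 7 undercount is therefore not F. It may well be larger.

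**The case against.** **Group matching is inferred.** Rules 1 and 2 name drugs, and no sentence says that a product listed under TZD or DPP4 cannot also satisfy them. Section 3.4.1 speaks of molecules. Table 5 does not follow Table 4 groups strictly: Lantus and Levemir are both basal analogs there, yet Lantus is in ranks 1 and 2 and Levemir in rank 3. This stands as a reason for caution. It does not repair the plan. The tracking sentence refers to product groups, Table 4 gives each combination one group, and no text tells the analyst to count a combination twice.

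**The rules are provisional.** They are to be finalised at study start, and a code list could sit in a later document. But the protocol does print a product table. A correction belongs there before the rules are frozen.

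**Over-estimation is already admitted.** Section 3.4.7 attributes it to stringent on-label rules in general. It does not mention combination products, and this part of the bias can be removed.

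**The TZD half is contestable.** The regulator asked about use with TZDs, TZD co-use is the secondary objective, and Table 1 does not name TZDs. A reader might infer from the pairs above that the two-tablet result is the right one and that TZD combinations belong on-label. The documents do not settle that. The pairs show only that the plan treats the same ingredients in two ways. This objection stands, and the fix must allow for it.

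**Conclusion.** The point holds as an inconsistency in how the plan's own rules 1 and 2 reach combination products. Read by product group, the same ingredients are on-label when filled separately and off-label when combined. This inflates inferred off-label use, and it undercounts the Metformin and SU rows of Table 7.

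Three stronger readings are tempting and not supported:

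- *Every patient whose only metformin or SU is in one of these tablets is mislabelled.* Not so: any Lantus script makes the patient on-label. A separate metformin or SU script also does so, anywhere from look-back to follow-up.
- *The off-label figure is too high by several percentage points.* The protocol gives no product shares and calls first-year Byetta use unknown. The 1% to 10% above is an assumption.
- *Table 7 is short by the same number.* It is not, for the reason in step 3.

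The conclusion rests on the assumed tablet contents, on matching by product group, and on the Table 5 footnote governing the evidence window. The rank 2 cohort description mentions only the analysis period. If that narrower window were applied, fewer patients would be spared.

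**What to change.** In Table 4, once the sponsor has confirmed the contents, map each combination product to all its components: Janumet to metformin and DPP4, Avandamet to metformin and TZD, Avandaryl to SU and TZD. State that Tables 5 and 7 both work from this ingredient-level mapping.

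Keep the TZD flag on Avandamet and Avandaryl. Report TZD co-use as its own count regardless of the ranked label, so that the remapping does not mask the secondary objective.

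Separately, the sponsor should reconcile the ranking of metformin or SU plus a TZD with the indication in Table 1. The mapping does not decide that question. Correct the table number in the sentence before Table 4 at the same time.

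The cost is one product-to-ingredient lookup and one extra reported count. No new data are needed.
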